### 13.3 STATISTICAL ANALYSIS

The changes implemented in the protocol amendment define, in addition to the original study population, 2 other groups of patients: a retrospective group and a group of patients from the Study DC4200C00058 whose RET data were re-analyzed with new classifications as positive and negative. The criteria for selecting these data, described elsewhere in this amended protocol, are intended to assure that the populations are comparable, and hence, may be pooled. In order to confirm comparability, all analyses will report the descriptive statistics for each of these groups as well as the pooled data both for RET mutation positive and RET mutation negative subjects, as presented in [Table 2](#).

Table content will adapt to the type of variable as defined below:

Qualitative variables will be described by number of observed values, percentage and number of missing values (patients with missing data will not be included in the percentage calculation).

Quantitative variables will be described by number of observed values, mean, standard deviation, median, first quartile, third quartile, minimum and maximum.

For time-to-event, the median time to event and, number and percentage of each group remaining at risk at the last point of observation will be provided.

Statistical analyses will be conducted with SAS Software version 9.3 or upper.

### **13.3.1 Analysis of primary criteria**

*Estimate ORR, DCR rates for RET positive and negative*

The ORR and DCR will be summarized as qualitative variables.

*Time to response and Duration of response for RET positive and negative*

The time to response and duration of response will be summarized as time-to-event data.

Kaplan-Meier curves will be produced. A waterfall plot of the best percentage change in the sum of the longest diameters of the target lesions from baseline will be produced split by RET mutation status.

### **13.3.3 Safety evaluation**

*Serious AE and AE leading to discontinuation – summary by RET mutation positive and RET mutation negative*

Safety data will be presented by RET mutation status. Caution will be used when interpreting safety data in RET negative patients who are not treated with vandetanib, that cannot be compared with safety data from the RET mutation negative patients who are treated with vandetanib.

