## PROTOCOL AMENDMENT SUMMARY OF CHANGES

### DOCUMENT HISTORY

Document	Country/countries impacted by amendment	Date, version
Amended Clinical Trial Protocol 02	All	21 June 2019, version 3.0 (electronic 2.0)
Amended Clinical Trial Protocol 01	All	29 February 2016, version 2.0 (electronic 1.0)
Original Protocol		11 March 2013, version 1

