### OVERALL RATIONALE FOR THE AMENDMENT

The Study D4200C00104 is conducted to fulfill the specific obligation (SOB) 001 post-authorization linked to the conditional marketing authorization of vandetanib (Caprelsa). The objective of Study D4200C00104 is to confirm in the real-life setting the benefit/risk ratio of vandetanib 300 mg, in both in Rearranged During Transfection (RET) mutation negative and RET mutation positive patients with symptomatic, aggressive, sporadic, unresectable, locally advanced/metastatic medullary thyroid cancer (MTC).

Recruitment started in 2014 (first patient in: 17 February 2014), had faced a number of challenges including the rarity of the disease under study, and the existing medical practice standards. These factors made clear the extreme scarcity of RET mutation negative patients and the low use of RET status in clinical practice. The initial sample size was to include 40 RET mutation positive and 40 RET mutation negative patients.

As of 02 Aug 2018, 34 patients were enrolled into Study D4200C00104. Twenty six were RET mutation positive and only 8 were RET mutation negative. No new prospective patients were included after 30 June 2017. On 15 June 2017, a meeting was held with the European medicines Agency (EMA), Committee for Medicinal Products for Human Use (CHMP) Rapporteur (France) and CHMP Co-Rapporteur (Netherlands) to discuss the SOB. During this meeting it was discussed that the Marketing Authorization Holder (MAH) believes there is no longer any scientific and clinical value in completing Study D4200C00104. Then, the EMA and CHMP (Co) Rapporteurs advised to submit a type II variation to request the switch from a conditional to a standard marketing authorization (not subject to SOBs) and to include the data

presented during the meeting in the variation dossier, as consequence Study D4200C00104 would be prematurely terminated.

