### **9.3.3 Deaths**

All deaths (both cancer-related and other) that occur during the study up to 60 days after the last dose received must be reported as a SAE. In the event of death, the patient will be considered as having completed the study.

All dead patients will be considered for the retrospective data collection, with no exception.

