#### 9.2.7 Disease progression

The following text has been added:

However, all events of disease progression that meet seriousness criteria must be reported using the SAE reporting procedure in Section 9.3.1.

In section(s):

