### **9.3.3 Deaths**

The following text:

All deaths (both cancer-related and other) that occur during the study must be reported as follows:

- Death clearly resulting from unequivocal disease progression should be reported to the study monitor at the next monitoring visit and should be documented on the relevant eCRF but should not be reported as an AE or SAE.
- When death is not due to progression of disease under study, the AE causing death must be reported to the study monitor as a SAE within 24 hours. The report should contain a comment regarding the co-involvement of progression of disease, if appropriate, and should assign main and contributory causes of death.

In the event of death, the patient will be considered as having completed the study.

Is replaced with:

All deaths (both cancer-related and other) that occur during the study up to 60 days after the last dose received must be reported as a SAE. follows:

- ~~Death clearly resulting from unequivocal disease progression should be reported to the study monitor at the next monitoring visit and should be documented on the relevant eCRF but should not be reported as an AE or SAE.~~
- ~~When death is not due to progression of disease under study, the AE causing death must be reported to the study monitor as a SAE within 24 hours. The report should contain a comment regarding the co-involvement of progression of disease, if appropriate, and should assign main and contributory causes of death.~~

In the event of death, the patient will be considered as having completed the study.

In section(s):

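### Reporting rules for progression events and progression deaths changed in February 2016, so pooled SAE incidence by RET status mixes two capture rules in unequal proportions

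*Protocol*

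**What the plan says.** Objective E in Section 2 includes the incidence of SAEs in vandetanib patients. Section 13.3.3 sets the display: "Safety data will be presented by RET mutation status". Its one caution about comparability concerns RET-negative patients who did not receive vandetanib.

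Section 13.3, with Table 2, has every analysis shown by data source (prospective, Study D4200C00058, retrospective) and pooled within each RET status. It expects the sources to be comparable enough to pool.

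The current reporting rules are in Sections 9.2.7 and 9.3.3. On progression: "However, all events of disease progression that meet seriousness criteria must be reported using the SAE reporting procedure in Section 9.3.1". On deaths, whether cancer-related or not, those "that occur during the study up to 60 days after the last dose received must be reported as a SAE".

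Section 14.2 dates both rules to Amendment 01, 29 February 2016. The progression sentence was new. The replaced text of 9.3.3 had said: "Death clearly resulting from unequivocal disease progression should be reported to the study monitor at the next monitoring visit". It required such deaths to be documented on the eCRF but kept them out of AE and SAE reporting. Section 9.1.2, the SAE definition, is not among the listed changes. The log is used here only to date a change in data capture; its difference from the current text is not a fault.

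The overall rationale for Amendment 02 gives the enrolment window: "first patient in: 17 February 2014" and "No new prospective patients were included after 30 June 2017". Of 34 patients enrolled, 26 were RET positive and 8 RET negative. Under Sections 3.1 and 4.2 only RET-negative patients can enter retrospectively, which became possible with Amendment 02 (21 June 2019).

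**The concern.** An incidence compared between two groups should count the same events in both. Here, a serious progression event or a progression death in 2015 was not an SAE, while the same event in 2017, or one abstracted from a chart after 2019, is. All of this study's RET-positive patients were enrolled across the change. The RET-negative group will consist largely of patients collected after it.

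The specific obligation reproduced in Appendix B is to confirm efficacy and safety in RET-negative patients. A difference in SAE incidence between the RET groups, or the absence of one, could therefore be read as a property of the drug in that population when part of it comes from reporting rules. Deaths are especially exposed: Section 10.2 expects that most retrospective patients may have died or left follow-up, and Section 9.3.3 brings all dead patients into consideration for the retrospective collection.

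**Working it through.** The protocol states no SAE rate or precision for this comparison, so there is no planned figure to reproduce. The enrolment counts agree: 26 + 8 = 34.

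**Step 1: where the change falls.** From 17 February 2014 to 29 February 2016 is 742 days. From 17 February 2014 to 30 June 2017 is 1229 days. 742 / 1229 = 60.4%, so 24.4 of 40.4 months of prospective inclusion precede the amendment date.

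**Step 2: make-up of the RET-negative group.** Section 3.1 plans 20 to 25 vandetanib-treated RET-negative patients. If all 8 prospective ones are treated (assumption), the retrospective number is 20 − 8 = 12 to 25 − 8 = 17, or 60% to 68% of the group. These fall wholly under the later rule.

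**Step 3: share starting under the earlier rule.** Assuming uniform accrual:

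- RET positive: 60.4%, about 16 of 26.
- RET negative: 0.604 × 8 = 4.8 patients, so 4.8 / 25 = 19% to 4.8 / 20 = 24%.
- Upper limit for RET negative, if all 8 enrolled before the change: 8 / 25 = 32% to 8 / 20 = 40%.

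The RET-positive share has no such limit from the documents. It depends on enrolment dates that are not given.

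**Step 4: prospective time under the earlier rule.** This is a simulation with uniform entry, exponential time on drug plus 60 days, and a cut-off either 14 months after the last prospective patient or at mid-2020. The medians are assumptions; 30.5 months is the predicted median PFS in Appendix B.

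| Median time on drug (months) | Share of prospective time before the amendment |
|---|---|
| 6 | 40% to 42% |
| 12 | 29% to 34% |
| 24 | 22% to 28% |
| 30.5 | 20% to 27% |

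**Step 5: illustrative effect on incidence.** Let o be the risk of a non-progression SAE, q the risk of a progression SAE or progression death, and s the share of progression events dated before the change. Recorded incidence = 1 − (1 − o) × (1 − q(1 − s)). For pooled RET negative, s is multiplied by 8/N. True risk is set equal in both groups.

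Example with o = 0.30, q = 0.20, s = 0.294 (median 12 months, mid-2020 cut-off), N = 20:

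- True incidence: 1 − 0.70 × 0.80 = 44.0%.
- RET positive: 1 − 0.70 × (1 − 0.20 × 0.706) = 39.9%.
- RET negative: s = 0.294 × 0.4 = 0.118; 1 − 0.70 × (1 − 0.20 × 0.882) = 42.4%.
- Gap: 2.5 points.

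With o fixed at 0.30, q from 0.10 to 0.40, medians from 6 to 30.5 months and N of 20 or 25, the gap runs from 0.8 points (35.6% against 36.4%) to 8.0 points (46.2% against 54.2%). With progression events and progression deaths excluded, q drops out and the gap from this source is zero.

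**Step 6: is the direction fixed?** Section 9.2.1 limits retrospective events to what the charts hold. In the example, retrospective incidence is 44.0% under full capture. If charts yielded only 39.9 / 44.0 = 91% of the patients with an SAE, the retrospective figure would equal the prospective one and the gap would vanish. Poorer capture would reverse it.

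**The case against.** The strongest reply is that Section 13.3 already shows each source in its own column. Prospective RET-positive and prospective RET-negative patients passed through the same change and can be read side by side. That stands, and it limits the problem. It does not remove it: the pooled columns keep the imbalance, the RET-positive retrospective column is empty by design, and Section 5.2 lets withdrawn prospective patients be reclassified as retrospective, for which only RET-negative patients qualify.

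Second, the comparison is descriptive and imprecise. With 20 to 25 per group and incidence near 50%, the 95% half-width for a difference is 1.96 × √(2 × 0.25 / n), or 31 to 28 points, well above the illustrative 1 to 8. This also stands and limits the weight of the point, but a known, removable bias need not be left in place because noise is larger.

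Third, the pooled columns also contain Study D4200C00058 patients, whose numbers and SAE rules are not stated in the statistical sections. The contrast is therefore not purely between two sources, and the calculation above ignores the third.

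Fourth, tabulation detail belongs in the SAP, which is not at hand. That is fair for layout. However, the protocol itself fixes the RET-status summary, asserts poolability and gives a comparability caution that omits this issue.

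A reader might go further in three ways that the documents do not support. One is that the SAE definition was widened: only Sections 9.2.7 and 9.3.3 changed, and the new death rule also added a 60-day limit. Another is that a RET-negative excess must appear by construction: Step 6 shows that the sign is open. The third is that SAE rates will seem to rise with time on drug: Section 13.3.3 plans no such display.

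**Conclusion.** The point holds in a limited form. The capture rule for serious progression events and progression deaths changed about 60% of the way through the prospective window, and only the RET-negative group contains patients collected entirely under the later rule. Pooled SAE incidence by RET status can therefore differ between groups partly because of reporting rules, and Section 13.3.3 neither separates nor mentions this.

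The 60% against 19% to 24% split assumes uniform accrual and that all 8 prospective RET-negative patients are treated. The 1 to 8 point gap further assumes equal true risk, the chosen event rates, exponential time on drug, full chart capture and adoption of the amendment on its document date. The protocol gives no site adoption dates and no enrolment or event dates by RET status, and does not say whether earlier events were re-collected. Actual size and net direction are therefore unknown. This is an inexpensive improvement to the safety summary, not evidence that its results will be wrong.

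**What to change.** In Section 13.3.3 and the synopsis:

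- Present SAEs by RET status and data source twice, including and excluding progression events and progression deaths, and base the pooled RET-group comparison on the version excluding them.
- Derive deaths within 60 days of the last dose for all patients from the recorded date and cause of death (Section 8.2), not from SAE reports. Progression deaths before the change were already to be documented on the eCRF, so they should be recoverable.
- State that non-fatal serious progression events before the change may be incompletely captured.

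Separately, reconcile Sections 9.2.7 and 9.2.8. The first sends serious progression events through the SAE procedure while saying that events unequivocally due to progression are not AEs. The second says metastasis and its symptoms are not reported as AE or SAE because they are progression. The progression flag needs one consistent reading.

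The cost is one extra table and a review of SAE terms to flag progression, since the variables in Section 9.2.3 include the verbatim term and probable cause of death but no dedicated field for non-fatal progression. No new patient data are needed. The downside is that the headline comparison no longer includes progression events; these remain visible in the companion table.

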## **14 SUPPORTING DOCUMENTATION AND OPERATIONAL CONSIDERATIONS**

### **14.1 COUNTRY-SPECIFIC REQUIREMENTS**

Not Applicable

### **14.2 PROTOCOL AMENDMENT HISTORY**

The Protocol Amendment Summary of Changes Table for the current amendment is located directly before the Table of Contents.

**Amended protocol 01:** (29 February 2016)

#### **REASON FOR AMENDMENT:**

#### **Genzyme assumption of responsibility for trial from AstraZeneca**

In sections: cover page, headers, appendices, and all sections of the protocol.

Rationale: In 2015, territory rights for the clinical development and commercialization of vandetanib were granted from AstraZeneca to Genzyme Corporation and Genzyme will be assuming responsibility of the current clinical program. Therefore, the AstraZeneca logo and reference to AstraZeneca within the confidentiality statement were deleted from the title page. Throughout all sections of the protocol including headers and appendices, AstraZeneca has been changed to “Genzyme” or “Sponsor.” The Sanofi-Genzyme study code OBS14778 has been added. Sections regarding IMP and pharmacovigilance have been updated to reflect the Genzyme environment.

#### **Correction of minor typographical errors or inconsistencies.**

#### **DESCRIPTION OF CHANGE AND WHAT IS BEING CHANGED:**

In section(s):

#### **Cover page**

The following text:

AstraZeneca AB, [name]

Is replaced with:

~~AstraZeneca AB, [name]~~ Genzyme Corporation, [name]

In section(s):

**Cover page and subsequent page headers**

The following text:

Study Code D4200C00104

Is replaced with:

Study Code D4200C00104 (Sanofi-Genzyme OBS14778)

In section(s):

**Study Synopsis**

**11.3 NIS timetable and end of study**

The following text:

Estimated date of first subject in	1Q2013
Estimated date of last subject in	2Q2014
Estimated date of last subject last visit	3Q2015
Estimated date of data base lock	3Q2015
Estimated date of final study report	4Q2015

Is replaced with:

Estimated date of first subject in	1Q2013
Estimated date of last subject in	<del>2Q2014</del> 2Q2018
Estimated date of last subject last visit	<del>3Q2015</del> 3Q2019
Estimated date of data base lock	<del>3Q2015</del> 4Q2019
Estimated date of final study report	<del>4Q2015</del> 3Q2020

In section(s):

List of abbreviations and definition terms

The following text is deleted:

AZ AstraZeneca

TCS Tata Consulting Service

In section(s):

**3 STUDY PLAN AND PROCEDURES**

**9.2.1 Time period for collection of adverse events**

**9.2.2 Follow-up of unresolved adverse events**

**9.3.1 Reporting of serious adverse events**

**9.3.2 Reporting of spontaneously mentioned adverse drug reactions**

**10.3 Patient data protection**

**11 STUDY MANAGEMENT BY ASTRAZENECA**

**11.1 Monitoring, Quality Control and Archiving**

**11.3 NIS timetable and end of study**

**12.2 Reporting and publication of data**

**13.1 Statistical evaluation – general aspects**

**13.2 Determination of sample size**

**Appendix E**

**Appendix F**

The following text:

AstraZeneca or AZ

Is replaced with:

AstraZeneca the Sponsor

In section(s):

**LIST OF ABBREVIATIONS AND DEFINITION OF TERMS**

The following text is added:

WHO-DD World Health Organization Drug Dictionary

Insection(s):

### 3.1 Overall study design and flow chart

#### Figure 1 Study Flow Chart

The following text:

~2 year recruitment period

Is replaced with:

~2 ~5 year recruitment period

In section(s):

#### 9.2.7 Disease progression

The following text has been added:

However, all events of disease progression that meet seriousness criteria must be reported using the SAE reporting procedure in Section 9.3.1.

In section(s):

#### 9.3.1 Reporting of serious adverse events

The following text:

If any SAE occurs in the course of the study, then Investigators or other site personnel inform appropriate Sponsor representatives within 1 day, ie, immediately, or no later than 24 hours of when he or she becomes aware of it.

The designated Sponsor representative works with the Investigator to ensure that all the necessary information is provided to the Sponsor Patient Safety data entry site (TCS) **within 1 calendar day** of initial receipt for fatal and life threatening events **and within 5 calendar days** of initial receipt for all other SAEs.

...

Once the Investigators or other site personnel indicate an AE is serious in the WBDC system, an automated e-mail alert is sent to the designated AstraZeneca representative and to the AstraZeneca Patient Safety data entry site (TCS).

If the WBDC system is not available, then the Investigator or other study site personnel reports a SAE to the appropriate AstraZeneca representative by telephone. The AstraZeneca representative will advise the Investigator/study site personnel how to proceed. If the system will not be available within the timeframes for SAE reporting, the SAE report form in the

Investigator study file shall be used. The eCRF must be completed with SAE information as soon as the WBDC system is available again.

Is replaced with:

If any SAE occurs in the course of the study, then Investigators or other site personnel inform appropriate Sponsor representatives within ~~1 day~~ **24 hours**, ie, immediately, ~~or no later than 24 hours of when he or she becomes aware of it.~~

The designated Sponsor representative works with the Investigator to ensure that all the necessary information is provided to the Sponsor ~~Patient Safety data entry site (TCS)~~ **within 1 calendar day** of initial receipt for fatal and life threatening events **and within 5 calendar days** of initial receipt for all other SAEs.

...

~~Once the Investigators or other site personnel indicate an AE is serious in the WBDC system, an automated email alert is sent to the designated AstraZeneca representative and to the AstraZeneca Patient Safety data entry site (TCS).~~

If a non-serious AE becomes serious, this and other relevant follow-up information must also be provided to the Sponsor within the timelines described above.

If the WBDC system is not available, then the Investigator or other study site personnel reports a SAE to the appropriate Sponsor representative by telephone. The Sponsor representative will advise the Investigator/study site personnel how to proceed. If the system will not be available within the timeframes for SAE reporting, the SAE report form in the Investigator study file shall be used. The eCRF must be completed with SAE information as soon as the WBDC system is available again.

In case of paper or fax CRF, or eCRF back-up:

- SEND (within 24 hours, preferably by fax or e-mail) the signed and dated corresponding page(s) from the CRF to the representative of the monitoring team whose name, fax number and e-mail address appear in the clinical trial protocol
- ATTACH a photocopy of all examinations carried out and the dates on which these examinations were performed. Care should be taken to ensure that the patient's identity is protected and the patient's identifiers in the clinical trial are properly mentioned on any copy of a source document provided to the Sponsor. For laboratory results, include the laboratory normal ranges
- All further documentation should be sent to the monitoring team within 24 hours of knowledge of the SAE. In addition, every effort should be made to further document any SAE that is fatal or life threatening within a week (7 days) of the initial notification.

In section(s):

